11.6.2. Clinical Laboratory Evaluation Analyses

Hematology, serum chemistry, and urinalysis parameters evaluated at each planned assessment, and changes from baseline at each planned post-baseline assessment, will be summarized by treatment. Shift tables (in categories of low, normal, and high, when appropriate) will be provided. Subjects with abnormal values will be identified in the data listings.

11.6.3. Vital Sign Analyses

Vital sign findings at each planned assessment, and changes from baseline at each planned post-baseline assessment, will be summarized.

11.6.4. Electrocardiogram Analyses

ECG data will be listed and summarized by visit. Shift tables for ECG results (normal or abnormal) will be presented by treatment arm to show changes from baseline (normal or abnormal) to end-of-treatment (normal or abnormal).

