12. Abnormal investigative tests (i.e. ECGs) and laboratory values judged by the investigator to be clinically significant at the End-of-Treatment visit (Visit 11, Week 13) in the preceding study (for rollover subjects) or at screening (for de novo subjects), with particular focus on:
 - Abnormal renal function defined as calculated CrCl < 60 mL/min determined by the central laboratory using the Cockcroft-Gault equation,⁴ blood urea nitrogen > 1.5 × ULN; serum creatinine > 1.6 mg/dL (> 141.4 μmol/L); or
 - Abnormal liver function defined as AST (SGOT) > 2.0 × ULN, ALT (SGPT) > 2.0 × ULN; alkaline phosphatase > 1.5 × ULN; total bilirubin > 1.2 × ULN. If a subject has total bilirubin > 1.2 ULN, unconjugated and conjugated bilirubin fractions should be analyzed and only subjects documented to have Gilbert's syndrome may be enrolled; or
 - Creatine kinase > 3.0 × ULN

For De Novo Subjects Only

13. Unable to undergo pre-study washout of prohibited concomitant medications (as listed in Section 5.2.1 of the protocol)
14. Current severe or uncontrolled major depressive disorder or anxiety disorders as assessed by the Mini-international Neuropsychiatric Interview (MINI) interview (Version 6.0) at screening are excluded, but mild to moderate major depression or

anxiety disorders are permitted provided that the investigator assesses the patient as clinically stable and appropriate for entry into the study

15. Any diagnosis of lifetime bipolar disorder or psychotic disorder
16. Subject is currently enrolled in or has not yet completed at least 30 days since ending another investigational device or drug study or is receiving other investigational agents
17. Subject is an employee of the study center, an immediate family member* of an employee of the study center, or an employee of Daiichi Sankyo, INC Research, or any of the study vendors supporting this study. *(spouse, parent, child, or sibling, whether biological or legally adopted)

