4.2.1. Reasons for Withdrawal/Early Discontinuation

If a subject discontinues from the study treatment for any reason, the reason for discontinuation or withdrawal must be recorded on the eCRF using the following criteria:

Subjects who did not complete one of the preceding Phase 3 DS-5565 studies (DS5565-A-E309, DS5565-A-E310, or DS5565-A-E311) and withdraw prior to start of treatment but after signing informed consent

- Did not satisfy all inclusion/exclusion criteria
- Adverse event
- Lost to follow-up
- Withdrawal by subject (indicate reason)
- Physician decision

For subjects discontinued or withdrawn after start of treatment but before completing the treatment period:

- Adverse event
- Death
- Lack of efficacy
- Lost to follow-up
- Protocol violation
- Study terminated by sponsor
- Withdrawal by subject (indicate reason)
- Other (indicate reason)

If a subject is withdrawn due to requirement for a prohibited pain medication, the reason may be recorded as lack of efficacy, as appropriate. Reasons recorded under "protocol violation" may include failure to comply with protocol requirements or study procedures, pregnancy, etc.

A subject may be withdrawn due to non-compliance with any aspect of the protocol, as determined by the investigator and/or the sponsor's medical monitor or designee. Subjects who miss > 7 days of consecutive doses of study medication should be withdrawn from the study and early termination study procedures performed.

All subjects who are withdrawn should complete protocol-specified withdrawal procedures (see Section 4.2.2 and Section 6.4).

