9. SAFETY ASSESSMENTS

9.1. Adverse Events

All clinical AEs (defined in Section 9.3) occurring after the subject has signed the ICF and up to 4 weeks after the last dose of study medication (i.e. the follow-up period), whether observed by the investigator or reported by the subject, will be recorded on the AE eCRF page. For subjects rolled over from a preceding study (DS5565-A-E309, DS5565-A-E310, or DS5565-A-E311), any AE that is ongoing at the start of this study will be recorded as an AE in this study, and all AEs (new or from a preceding study) will be followed until resolution. For these rolled-over subjects, all AEs will be evaluated in the context of their experience in the preceding study.

All laboratory, vital sign, or ECG values should be appraised by the investigator as to clinical significance. Isolated abnormal laboratory results, vital sign findings, or ECG findings should be reported as AEs if they are symptomatic, lead to study drug discontinuation, require corrective treatment, or are otherwise defined as an adverse event of special interest (AESI) [please refer to Section 9.2].

All SAEs are to be reported according to the procedures in Section 9.4 (SAE Reporting-Procedure for Investigators). Always report the diagnosis as the AE or SAE term. When a diagnosis is unavailable, report the primary sign or symptom as the AE or SAE term with additional details included in the SAE narrative until the diagnosis becomes available. If the signs and symptoms are distinct and do not suggest a common diagnosis, report as individual entries of AE or SAE. For events that are serious due to hospitalization, the reason for hospitalization must be reported as the SAE (diagnosis or symptom requiring hospitalization). Pre-planned (prior to signing the ICF) procedures or hospitalizations for pre-existing conditions which do not worsen in severity should not be reported as SAEs (see Section 9.3 for Definitions). For deaths, the underlying or immediate cause of death should always be reported as an SAE. In addition, any serious, untoward event that may occur subsequent to the reporting period that the Investigator assesses as related to study drug should also be reported and managed as an SAE.

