9.8. Electrocardiograms

A 12-lead ECG will be conducted at the Screening visit (Visit 1) for de novo subjects, and at Start-of-Treatment visit (Visit 4) and at the End-of-Treatment/Early Termination visit (Visit 21) for all subjects. ECG recordings should be assessed as normal or abnormal, and any abnormal findings should be assessed as not clinically significant or significant. Clinically significant abnormal findings should be reported as medical history (if pre-existent). Refer to Section 9.1 for general guidance on when to report abnormal findings as AEs.

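### The ECG shift table in 11.6.4 leaves out the clinical-significance grade that 9.8 collects, so it cannot count new clinically significant abnormalities; the end-of-treatment and baseline ECGs also need defining

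*Combined protocol and SAP*

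**What the plan says.** ECG is a named component of the primary safety endpoint (3.1.3).

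- **Grading.** Section 9.8: "ECG recordings should be assessed as normal or abnormal, and any abnormal findings should be assessed as not clinically significant or significant". That gives three levels: normal, abnormal NCS, abnormal CS.
- **Analysis.** Section 11.6.4 has two sentences. The first: "ECG data will be listed and summarized by visit". It does not name the categories of the by-visit summary. The second: "Shift tables for ECG results (normal or abnormal) will be presented by treatment arm to show changes from baseline (normal or abnormal", and it goes on to use normal or abnormal again for the end-of-treatment reading.
- **Timing.** Section 9.8 schedules ECGs at screening for de novo subjects, and "at Start-of-Treatment visit (Visit 4) and at the End-of-Treatment/Early Termination visit (Visit 21) for all subjects". Visit 21 is therefore the only scheduled post-baseline ECG, and it serves both completers and subjects who stop early.
- **Route into the adverse event tables.** Section 9.1: "Isolated abnormal laboratory results, vital sign findings, or ECG findings should be reported as AEs if they are symptomatic, lead to study drug discontinuation", or if they call for treatment or are events of special interest.
- **Entry.** Exclusion 12 in 4.1.2 bars "Abnormal investigative tests (i.e. ECGs) and laboratory values judged by the investigator to be clinically significant at the End-of-Treatment visit" of the preceding study (rollover subjects) or at screening (de novo subjects).
- **Missed doses.** Section 4.2.1: "Subjects who miss > 7 days of consecutive doses of study medication should be withdrawn from the study and early termination study procedures performed".

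**The concern.** The shift table is the only within-subject ECG analysis that the plan specifies, and it rests on one scheduled post-baseline recording. The investigator's judgement of clinical significance is what separates an incidental abnormality from one that matters for safety. The plan collects that judgement and then leaves it out of the table meant to show change. A subject who goes from NCS to CS is shown as unchanged. A subject who goes from normal to CS is pooled with subjects who acquired an incidental finding. A reader of the study report could see a reassuring table, or an alarming one, and be unable to tell which it is.

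A second gap concerns what the end-of-treatment column contains. If recordings made well after the last dose enter it without a label, they may weaken any on-treatment ECG signal.

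**Working it through.** The plan states no figure on this point, and no power or error-rate calculation applies: the analyses are descriptive (Synopsis, Statistical Analyses). The check is a count of transitions and a comparison of sections.

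**1. Collapse of the grades.** Three collected levels at two times give 3 x 3 = 9 transitions. Two tabulated levels give 2 x 2 = 4 cells.

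| Planned cell | Transitions it contains | Count |
|---|---|---|
| Normal to normal | N-N | 1 |
| Normal to abnormal | N-NCS, N-CS | 2 |
| Abnormal to normal | NCS-N, CS-N | 2 |
| Abnormal to abnormal | NCS-NCS, NCS-CS, CS-NCS, CS-CS | 4 |

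The total is 1 + 2 + 2 + 4 = 9. A new CS abnormality is N-CS or NCS-CS. Each is merged with other transitions, so the planned table bounds the number of new CS cases only between zero and everyone abnormal at end of treatment.

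**2. What sits in the abnormal baseline row.** Exclusion 12 removes subjects with CS ECGs, so that row should be mostly NCS, and the main adverse change within it is NCS to CS. This is plausible but not guaranteed. For rollover subjects the exclusion looks at the preceding study's End-of-Treatment visit (Week 13), while 9.8 schedules a separate ECG at Visit 4, and 11.6.4 does not say which ECG is baseline.

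**3. Whether another output supplies the count.**

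- *Listing:* can show the grade for each subject, but gives no number or percent.
- *By-visit summary:* categories unstated. If it included the grade, CS at Visit 21 minus CS at baseline would give new cases minus resolved cases in subjects with both ECGs. That equals the number of new cases only if nobody is CS at baseline, and it would not show whether they began normal or NCS.
- *Adverse event tables:* clinical significance alone is not one of the triggers in 9.1. By contrast, 11.6.5 makes clinically significant physical examination findings adverse events; 11.6.4 has no matching sentence.

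**4. The end-of-treatment ECG.** Completers take their last dose the evening before Visit 21 (6.3). Withdrawn subjects have Visit 21 procedures as soon as possible, with no maximum interval from last dose (4.2.2). A subject withdrawn under the missed-dose rule has already gone more than 7 days without drug, unless dosing restarted before the lapse was found. Section 11.6.4 does not say whether such a recording is an end-of-treatment ECG.

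**5. The Visit 4 ECG.** Section 9.8 and Table 17.1 require it for all subjects. The rollover list in 6.2.1 includes it; the de novo list in 6.2.2 does not. A site following 6.2.2 would leave a de novo subject with only the screening ECG before treatment.

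**The case against.** The strongest reply is that 11.6.4 is a protocol-level summary. Section 11.2 promises a detailed SAP, the grade is in the database, and the ECG data will be listed and summarized by visit. This stands in part: the loss is confined to one cross-tabulation. A reader might infer that clinically significant worsening would go unreported altogether; the documents do not support that. But 11.6.4 is not silent on the table. It fixes the two categories, and an SAP that followed it would carry them forward. The laboratory shift tables in 11.6.2, at the same level of detail, use three.

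It can also be said that the adverse event route is wider than it looks. The limit in 9.1 concerns isolated findings, 9.3.1 leaves the decision to the investigator, and 6.5.1.2 has abnormal end-of-treatment findings rechecked at follow-up. That narrows the gap to CS findings that are asymptomatic, untreated and do not lead to discontinuation. It does not close it.

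On timing, a reader might infer that off-drug early-termination ECGs count as end of treatment. No section says so. The shared visit makes it likely, but the supportable statement is that inclusion and the maximum interval are undefined.

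Finally, a reader might try to size the problem by applying a guessed rate of abnormal ECGs to 500 subjects. Neither part is supported: the documents contain no ECG rates, and 500 is a goal for subjects exposed at least 52 weeks (11.11), whereas safety analyses use all subjects with at least one dose (11.1, 11.6).

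**Conclusion.** The point holds for the shift table. Followed exactly, 11.6.4 shows NCS-to-CS worsening as no change and cannot distinguish normal-to-CS from normal-to-NCS, although 9.8 collects what is needed. This follows from the text and needs no assumption about rates. The number of subjects affected cannot be calculated from the documents. The effect is on descriptive reporting of one component of the primary safety endpoint; no error rate, power or sample size changes.

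The timing point is secondary and is a gap in definition, not a demonstrated error. The mismatch between 6.2.2 and 9.8 with Table 17.1 is a plain inconsistency, and it bears on which ECG serves as baseline.

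**What to change.** 1. In 11.6.4 and the SAP, replace the two-category table with a 3 x 3 shift (normal / abnormal NCS / abnormal CS) from baseline to end of treatment in the safety set, and report the number and percent of subjects with a new CS abnormality.
2. Define the end-of-treatment ECG. State whether early-termination recordings are included and up to what interval after last dose, or show later ones separately as post-treatment. The sponsor should set the window and give its reason; the documents offer no basis for a particular number of days.
3. State which ECG is baseline for rollover and for de novo subjects.
4. Reconcile 6.2.2 with 9.8 and Table 17.1 on the de novo Visit 4 ECG.

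Items 1 to 3 cost table and SAP wording. The grade is already collected, the date of last treatment is recorded for withdrawals (4.2.2), and 11.2 lets deviations from the protocol's planned analyses be described in the SAP unless they substantively alter its principal features. Item 4 changes protocol text. Nothing here adds an ECG beyond those 9.8 already schedules.

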11.6.5. Physical Examinations

Clinically significant abnormal physical examination findings will be reported as AEs. Data from physical examinations will be listed and summarized by visit.

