6.3. On-Treatment Period (Visits 5 to 20; Weeks 1 to 48)

The following activities and/or assessments will be performed at all On-Treatment visits (except where otherwise noted):

- Assess for and record AEs
- After 3 weeks on the 15 mg QD dose (at Visit 6, Week 3), subjects will be asked about the adequacy of their pain control and may be dose-escalated to DS-5565 15 mg BID (see Section 5.1.1)
- Assess for and record concomitant medication use including allowable analgesics
- Review instructions with the subject for completion of the pain and sleep interference diary. Note: These instructions need to be reviewed with the subject only at Visit 10 (Week 11), Visit 13 (Week 20), Visit 16 (Week 32), Visit 19 (Week 44), and Visit 20 (Week 48)
- Review electronic diary data from the previous week. Note: These data need to be reviewed only at Visit 11 (Week 13), Visit 14 (Week 24), Visit 17 (Week 36), Visit 20 (Week 48), and Visit 21 (Week 52)
- Collect study medication wallets and review medication compliance
- Record vital signs (temperature, heart rate, supine and orthostatic blood pressure) and body weight
- Complete the C-SSRS and evaluate for continued eligibility (See Section 9.2.1)
- Perform an abbreviated physical examination for all subjects; perform a funduscopy examination without pupil dilation or a scanning laser ophthalmoscopy examination at Visit 14 (Week 24) for de novo subjects (see Section 9.9.2)
- Collect non-fasting blood and urine samples for evaluation of standard laboratory safety tests (chemistry, hematology, and urinalysis). The central laboratory will perform a serum pregnancy test on all female subjects regardless of child-bearing potential
- Contact IXRS and obtain new study medication wallet number (as needed)
- Dispense study medication and review dosing instructions. At Visit 20 (Week 48), subjects should be instructed to take all study medication, as scheduled, up until the day of their End-of-Treatment visit (Visit 21, Week 52), but not on the morning of Visit 21 (i.e. subjects should complete dosing on the evening prior to their End-of-Treatment visit)

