6.4. End-of-Treatment/Early Termination (Visit 21; Week 52)

The following activities and/or assessments will be performed at the End-of-Treatment or Early Termination visit (Visit 21). No fasting is required prior to the End-of-Treatment visit.

- Assess for and record AEs
- Assess for and record concomitant medication use including allowable analgesics
- Review electronic diary data and collect electronic diary
- Collect study medication and review medication compliance
- Record vital signs (temperature, heart rate, supine and orthostatic blood pressure) and body weight
- Collect blood and urine samples for evaluation of standard laboratory safety tests (chemistry [hematology, and urinalysis). The central laboratory will perform a serum pregnancy test on all female subjects regardless of child-bearing potential
- Ask the subject to complete the PGIC, HADS, SF-36 and EQ-5D questionnaires
- Complete the C-SSRS (See Section 9.2.1)
- Perform complete physical examination for all subjects, including a fundoscopy examination with pupil dilation or a scanning laser ophthalmoscopy examination for de novo subjects only (see Section 9.9.2)
- Perform a 12-lead ECG (Section 9.8)
- Update IXRS with subject status

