9.9.2. Physical Examinations

A full physical examination, with the exception of pelvis, breast, and rectum in women and the genitourinary system and prostate in men, will be performed at the Screening visit (Visit 1) for de novo subjects or at the Start-of-Treatment visit (Visit 4) for rollover

subjects and End-of-Treatment/Early Termination visit (Visit 21) for all subjects. An abbreviated physical examination will be performed at the Treatment visits.

The full physical examination should minimally include clinical evaluations of the head, neck, thyroid, eyes, ears, nose, throat, heart, lungs, lymph nodes, abdomen, skin, extremities, and musculoskeletal system.

For de novo subjects, a fundoscopy examination of the eyes, with pupil dilation or a scanning laser ophthalmoscopy examination, will be conducted at the Screening visit (Visit 1) and End of Treatment visit (Visit 21) during the full physical examination. At Visit 14 (Week 24), the abbreviated physical examination will include a fundoscopy examination without pupil dilation or a scanning laser ophthalmoscopy examination.

The abbreviated physical examination should minimally include clinical evaluations of the heart and lungs. Additional systems may be examined based on any symptoms exhibited by the subject.

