11.2. General Statistical Considerations

The statistical package SAS[®] (Version 9.2 or higher) will be used to produce all summary tables and figures and data listings.

Raw data will be presented with the same precision with which they were collected.

For summary statistics, means and medians will be displayed to one more decimal place than was determined for raw data, dispersion statistics will have two more decimal places, and the minimum and maximum will be displayed to the same number of decimal places as the raw data.

Quantitative data will be tabulated with descriptive summary statistics: arithmetic mean, standard deviation, median, minimum and maximum values, and number of observations. For categorical data, frequency tables will be provided.

For variables expressed as percent, the denominators for the calculation of percentage will be the number of subjects who had that variable assessed.

A detailed SAP describing the methodology to be used in the final analysis will be prepared before data unblinding. A change in the planned statistical analysis will require a protocol amendment only if it substantively alters the principal features of the protocol. Any deviations from the planned statistical analyses in the protocol will be fully described in the SAP.

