11.6. Safety Analyses

The safety analysis set will be used for all safety analyses. For safety endpoints, the data from AE assessments, clinical laboratory assessments, physical examinations, 12-lead ECGs, vital signs (including weight) assessments, the C-SSRS evaluation, and the PWC evaluations will be summarized. Preceding study and extension study data will be summarized separately and also may be combined.

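### Fundus examinations are scheduled only in de novo subjects, but TEAEs are tabulated over everyone dosed, so the TEAE percentage for symptomless fundus findings is biased low

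*Combined protocol and SAP*

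**What the plan says.** **Who is examined.** Protocol section 9.9.2 covers Visits 1 and 21: "For de novo subjects, a fundoscopy examination of the eyes, with pupil dilation or a scanning laser ophthalmoscopy examination, will be conducted" as part of the full physical examination. Section 6.3 adds fundoscopy without dilation or a "scanning laser ophthalmoscopy examination at Visit 14 (Week 24) for de novo subjects". Section 6.4 limits the Visit 21 examination to fundoscopy with dilation or a "scanning laser ophthalmoscopy examination for de novo subjects only". Table 17.1 gives fundoscopy its own row and marks all three visits as de novo only.

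**What rollover subjects have.** Under section 9.9.2 they have a full physical examination at Visits 4 and 21, and the eyes are among its minimum components. No fundus examination is scheduled for them in this study.

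**How findings are reported.** Section 11.6.5: "Clinically significant abnormal physical examination findings will be reported as AEs". The same section also sends the examination data to listings and by-visit summaries. Section 11.6: "The safety analysis set will be used for all safety analyses". Section 11.1 defines that set as all subjects with at least one dose, whatever their route of entry. Section 11.6.1 tabulates TEAEs by system organ class, preferred term, seriousness, worst severity and relationship. Section 11.3 splits demographics and disposition by preceding-study assignment where applicable, but section 11.6.1 has no such split and none by entry cohort.

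**Denominator rule.** Section 11.2: "the denominators for the calculation of percentage will be the number of subjects who had that variable assessed".

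**The concern.** A fundus finding that causes no symptoms, and that a general look at the eyes would miss, is found only if someone examines the fundus. In this study that happens on schedule in one entry cohort. The finding then becomes an AE and is counted over both cohorts. Barring unscheduled examinations, rollover subjects add to the denominator of that percentage and nothing to its numerator.

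The resulting figure depends on the mix of de novo and rollover subjects as well as on the drug. Long-term safety is the primary endpoint (section 3.1.3), and section 1.3 lists ophthalmologic disorders among the cautions for approved drugs of this class. A low percentage in the TEAE table, or none at all, could be read as evidence about all dosed subjects when only part of them were examined in a way that could show the finding.

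**Working it through.** The documents give no rate, denominator or precision for eye findings, so there is no planned figure to reproduce. The check is of the reporting chain and of the size of the effect under stated assumptions.

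**Inputs**
- Scheduled fundus examination: de novo subjects only (sections 6.1.1, 6.3, 6.4, 9.9.2; Table 17.1).
- TEAE denominator: all dosed subjects (sections 11.1, 11.6).
- r, the rollover share of the safety set: not stated; assumed.
- s, the share of such findings in rollover subjects that surface without the scheduled examination (for example at an unscheduled examination): not stated; assumed.
- p, the true rate of treatment-emergent, clinically significant findings that the scheduled fundus examinations detect and that would otherwise be symptomless: not stated; assumed equal in both cohorts, with all de novo subjects examined.

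**Does the rule in section 11.2 repair the denominator?** AE status is collected in every subject, so for a TEAE the subjects assessed are everyone dosed. The rule leaves the TEAE denominator as it is. It does help the by-visit summary: if fundoscopy is summarized as its own variable, only examined subjects count.

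**Dilution.** With N dosed subjects, the expected number of reported findings is N(1−r)p from de novo subjects and N·r·p·s from rollover subjects. Dividing by N and then by p:

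reported/true = (1−r) + r·s

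| r | s = 0 | s = 0.5 | an assumed true 5% is reported as (s = 0) |
|---|---|---|---|
| 20% | 0.80 | 0.90 | 4% |
| 50% | 0.50 | 0.75 | 2.5% |
| 80% | 0.20 | 0.60 | 1% |

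The ratio moves towards 1 as r falls or s rises. At r = 10%, s = 0.5 it is 0.90 + 0.05 = 0.95. At r = 20%, s = 0.8 it is 0.80 + 0.16 = 0.96.

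**If no finding is seen.** The exact one-sided 95% upper bound for 0 out of m is 1 − 0.05^(1/m). Take 500 dosed subjects as an illustration; section 11.11 gives about 500 as the goal for 52-week exposure, not as the size of the safety set. Then 0/500 gives 0.60%. If only 250, 125 or 50 of them had a fundus examination, the bound the data support is 1.19%, 2.37% or 5.82%.

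**The case against.** The strongest case on the other side has four parts.

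1. **Rollover subjects do have their eyes looked at.** A reader might infer that they are never examined, or that the fundus examinations are the study's only scheduled look at the eyes. Section 9.9.2 does not support either: the full physical examination at Visits 4 and 21 includes the eyes, and eye AEs can be recorded at any visit. What rollover subjects lack is a scheduled fundus examination in this study. The documents do not say whether the preceding studies included one. This objection stands, and it confines the point to findings that need a fundus examination.

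2. **The examination summary may be sound.** A reader might infer that the by-visit summary is diluted as well. The documents do not describe an entry that merges fundoscopy with the general eye evaluation, and Table 17.1 keeps them on separate rows. If fundoscopy is summarized as its own variable, section 11.2 already gives the right denominator. Section 11.6.5 does not say that it will be, so the wording should be settled, but the bias shown here is in the TEAE table.

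3. **The size is assumed.** This stands in full. The values of r, s and p have no source in the documents, and there is no fixed minimum bias. The 2100 to 2500 subjects in section 11.11 are anticipated completers who could roll over, not an enrollment figure, and entry stops once the exposure goal looks attainable. That figure does not show that r is high.

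4. **A detailed SAP is still to come.** Section 11.2 promises one and section 11.6.1 leaves the AEs of special interest to it. It could contain an eye table by entry cohort. That possibility lowers the urgency. It does not close the gap, because nothing in section 11 mentions fundoscopy, and section 9.2 describes only suicidality and liver events as of special interest.

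**Conclusion.** The point holds in a narrow form. Following the stated rules, the TEAE percentage for symptomless findings detectable only by fundus examination is biased low, because one cohort is examined on schedule and both are counted. The direction follows from the documents whenever there are rollover subjects and some of their findings go undetected.

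The size does not follow from the documents. Assuming equal true rates and s = 0, the reported percentage is 80%, 50% or 20% of the true one at rollover shares of 20%, 50% or 80%. With few rollover subjects, or with most findings surfacing anyway, the bias is small.

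A reader might go further and conclude that eye-disorder TEAE rates in general are diluted. The documents do not support that: symptomatic eye events can be reported by every subject. The study is descriptive and no test depends on this percentage. The matter is still worth correcting, because the affected table serves the primary endpoint and the correction is cheap.

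**What to change.** **Section 11.6.5.** Add wording to this effect:

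> Fundoscopy and scanning laser ophthalmoscopy results will be summarized as a separate variable, as new or worsened from the pre-treatment examination. The denominator will be de novo subjects with a pre-treatment and at least one post-baseline fundus examination. The number examined and the method used will be shown at each visit. Fundus findings from unscheduled examinations in rollover subjects will be listed separately.

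The method needs to be shown because fundoscopy at Visit 14 is undilated, while at Visits 1 and 21 it is dilated; scanning laser ophthalmoscopy is an alternative at all three. The text should also say which examination counts as pre-treatment, since the de novo inclusion criteria accept one from the 12 months before screening while section 9.9.2 schedules one at Visit 1.

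**Section 11.6.1.** Present eye-disorder TEAEs by entry cohort (de novo, rollover), with a footnote that only de novo subjects had scheduled fundus examinations in this study.

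**Cost.** One extra table and a cohort split, from data already collected. There is no new visit or procedure. The price is a smaller denominator and wider uncertainty for fundus findings, which reflects how many subjects were examined. If the detailed SAP already contains such a table, a cross-reference in section 11.6.5 is enough.
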